8.2 SAFETY ASSESSMENTS

No physical examinations, performance tests, imaging, biospecimen collection, special assays, sensors, or EMA are performed by the study. Safety procedures consist of: (1) AE/SAE identification and follow-up; (2) monitoring for distress potentially triggered by educational content; and (3) privacy/technology safeguards (e.g., wrong-number texting, shared phones). AEs are any unfavorable or unintended psychological or practical effect temporally associated with participation in the study's activities (videos, SMS, surveys), whether or not considered related. Examples include: heightened anxiety/distress about CRC risk, dissatisfaction with messaging frequency, perceived breach of privacy (e.g., texts seen by others on a shared device), or escalation of medical mistrust that prompts clinical concern. SAEs would be rare in this context and are defined per IRB policy (e.g., death, life-threatening event, hospitalization) regardless of attribution.

8.3 ADVERSE EVENTS AND SERIOUS ADVERSE EVENTS

No text is to be entered in this section; rather it should be included under the relevant subheadings below.

8.3.1 DEFINITION OF ADVERSE EVENTS

An AE is defined as an event that is unexpected, related or possibly related to research participation, and suggests that the research places subjects or others at a greater risk of harm than was previously known or recognized.

8.3.2 DEFINITION OF SERIOUS ADVERSE EVENTS

An SAE is defined as an event that results in death, is life-threatening, results in inpatient hospitalization or prolongation of existing hospitalization, results in persistent or significant disability/incapacity, results in a congenital anomaly/birth defect, or may jeopardize the subject's health and may require medical or surgical intervention to prevent one of the other outcomes listed.

8.3.3 CLASSIFICATION OF AN ADVERSE EVENT

No text is to be entered in this section; rather it should be included under the relevant subheadings below.

8.3.3.1 SEVERITY OF EVENT

For adverse events (AEs) not included in the protocol defined grading system, the following guidelines will be used to describe severity.

- **Mild** – Events require minimal or no treatment and do not interfere with the participant's daily activities.
- **Moderate** – Events result in a low level of inconvenience or concern with the therapeutic measures. Moderate events may cause some interference with functioning.
- **Severe** – Events interrupt a participant's usual daily activity and may require systemic drug therapy or other treatment. Severe events are usually potentially life-threatening or incapacitating. Of note, the term "severe" does not necessarily equate to "serious".

8.3.3.2 RELATIONSHIP TO STUDY INTERVENTION/EXPERIMENTAL MANIPULATION

All adverse events (AEs) will have their relationship to study procedures, including the intervention, assessed based on temporal relationship. The degree of certainty about causality will be graded using the categories below.

- **Related** – The AE is known to occur with the study procedures, there is a reasonable possibility that the study procedures caused the AE, or there is a temporal relationship between the study procedures and the event. Reasonable possibility means that there is evidence to suggest a causal relationship between the study procedures and the AE.

- **Not Related** – There is not a reasonable possibility that the study procedures caused the event, there is no temporal relationship between the study procedures and event onset, or an alternate etiology has been established.

8.3.3.3 EXPECTEDNESS

A member of the research team with appropriate expertise will be responsible for determining whether an adverse event (AE) is expected or unexpected. An AE will be considered unexpected if the nature, severity, or frequency of the event is not consistent with the risk information previously described for the study procedures.

8.3.4 TIME PERIOD AND FREQUENCY FOR EVENT ASSESSMENT AND FOLLOW-UP

The occurrence of an adverse event (AE) or serious adverse event (SAE) may come to the attention of study personnel during study appointments.

All AEs, not otherwise precluded per the protocol, will be captured on the appropriate case report form (CRF). Information to be collected includes event description, time of onset, assessment of severity, relationship to study procedures (assessed only by those with the training and authority to make a diagnosis), and time of resolution/stabilization of the event. All AEs occurring while on study will be documented appropriately regardless of relationship. All AEs will be followed to adequate resolution.

Any medical or psychiatric condition that is present at the time that the participant is screened will be considered as baseline and not reported as an AE. However, if the study participant's condition deteriorates at any time during the study, it will be recorded as an AE.

Changes in the severity of an AE will be documented to allow an assessment of the duration of the event at each level of severity to be performed. Documentation of onset and duration of each episode will be maintained for AEs characterized as intermittent.

The study coordinator will record events with start dates occurring any time after informed consent is obtained until 7 (for non-serious AEs) or 30 days (for SAEs) after the last day of study participation. At each study visit, the investigator will inquire about the occurrence of AE/SAEs since the last visit. Events will be followed for outcome information until resolution or stabilization.

8.3.5 ADVERSE EVENT REPORTING

Any AE or SAE, whether or not related to study intervention, will be reported to the IRB, NCI, and the Office for Human Research Protections (OHRP). SAE's will be reported to the IRB within 24 hours and AEs will be reported to the IRB within 72 hours. All SAE's and AE's will be reported to NCI and OHRP within two weeks. The initial report will be followed by submission of a completed report to all institutions.

8.3.6 SERIOUS ADVERSE EVENT REPORTING

Any AE or SAE, whether or not related to study intervention, will be reported to the IRB, NCI, and the Office for Human Research Protections (OHRP). SAE's will be reported to the IRB within 24 hours and AEs will be reported to the IRB within 72 hours. All SAE's and AE's will be reported to NCI and OHRP within two weeks. The initial report will be followed by submission of a completed report to all institutions.

8.3.7 REPORTING EVENTS TO PARTICIPANTS

N/A

8.3.8 EVENTS OF SPECIAL INTEREST

N/A

8.3.9 REPORTING OF PREGNANCY

N/A

8.4 UNANTICIPATED PROBLEMS

No text is to be entered in this section; rather it should be included under the relevant subheadings below.

8.4.1 DEFINITION OF UNANTICIPATED PROBLEMS

This protocol uses the definition of Unanticipated Problems as defined by the Office for Human Research Protections (OHRP). OHRP considers unanticipated problems involving risks to participants or others to include, in general, any incident, experience, or outcome that meets all of the following criteria:

- Unexpected in terms of nature, severity, or frequency given (a) the research procedures that are described in the protocol-related documents, such as the Institutional Review Board (IRB)-approved research protocol and informed consent document; and (b) the characteristics of the participant population being studied;
- Related or possibly related to participation in the research (“possibly related” means there is a reasonable possibility that the incident, experience, or outcome may have been caused by the procedures involved in the research); and
- Suggests that the research places participants or others at a greater risk of harm (including physical, psychological, economic, or social harm) than was previously known or recognized.

8.4.2 UNANTICIPATED PROBLEMS REPORTING

The investigator will report unanticipated problems (UPs) to the reviewing Institutional Review Board (IRB). The UP report will include the following information:

- Protocol identifying information: protocol title and number, PI's name, and the IRB project number
- A detailed description of the event, incident, experience, or outcome
- An explanation of the basis for determining that the event, incident, experience, or outcome represents an UP
- A description of any changes to the protocol or other corrective actions that have been taken or are proposed in response to the UP

To satisfy the requirement for prompt reporting, UPs will be reported using the following timeline:

- UPs that are serious adverse events (SAEs) will be reported to the IRB within 24 hours and to the funding agency within two weeks of the investigator becoming aware of the event
- Any other UP will be reported to the IRB within 72 hours and to the funding agency within two weeks of the investigator becoming aware of the problem
- All UPs should be reported to appropriate institutional officials (as required by an institution's written reporting procedures), the supporting agency head (or designee), and the Office for Human Research Protections (OHRP) within two weeks of the IRB's receipt of the report of the problem from the investigator.

8.4.3 REPORTING UNANTICIPATED PROBLEMS TO PARTICIPANTS

N/A

9 STATISTICAL CONSIDERATIONS

No text is to be entered in this section; rather it should be included under the relevant subheadings below.

9.1 STATISTICAL HYPOTHESES

- Primary Endpoint(s):

We hypothesize that, compared to participants who receive standard educational materials via SMS (control), participants who receive the tailored mobile video+SMS intervention (m-CRCSi) will have a higher proportion completing any guideline-concordant colorectal cancer (CRC) screening within 6 months post-randomization. Alternatively, our null hypothesis is that there will be no difference between arms in screening completion at 6 months.

- Secondary Endpoint(s):

Self-reported proxy screening composite (6 months):

We hypothesize that the intervention arm will report a higher rate of any guideline-concordant CRC screening by 6 months than the control arm; the null hypothesis is that there will be no difference between arms.

CRC knowledge (baseline→6 months):

We hypothesize that intervention participants will show greater improvement in CRC knowledge from baseline to 6 months than control participants; the null hypothesis is that there will be no difference in change between arms.

Perceived susceptibility and severity (baseline→6 months):

We hypothesize that intervention participants will report greater increases in perceived susceptibility and severity from baseline to 6 months than control participants; the null hypothesis is that there will be no difference in change between arms.

Perceived benefits and barriers for colonoscopy and stool testing (baseline→6 months):

We hypothesize that intervention participants will report greater increases in perceived benefits and greater decreases in perceived barriers from baseline to 6 months than control participants; the null hypothesis is that there will be no difference in change between arms.

Medical trust (baseline→6 months):

We hypothesize that intervention participants will report greater increases in trust in the medical profession from baseline to 6 months than control participants; the null hypothesis is that there will be no difference in change between arms.

Self-efficacy (overall; colonoscopy; stool test) and advocacy (baseline→6 months):

We hypothesize that intervention participants will demonstrate greater improvements from baseline to 6 months than control participants; the null hypothesis is that there will be no difference in change between arms.

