9.2 SAMPLE SIZE DETERMINATION

To determine the adequate sample size for our study, we examined achieved power and treatment effects for a study examining the efficacy of a conceptually similar intervention with an equivalent data analysis plan. Specifically, Miller et al. developed a digital decision aid to help patients select a CRC screening test before a primary care appointment. Compared to controls, participants assigned to the decision aid were twice as likely to get screened at 6-month followup (30% [67/223] vs. 15% [34/227], difference=15%, 95% CI 7% to 23%; OR = 2.5). Follow-up analyses with only nonwhite participants continued to show a significant positive effect on screening (34% [33/98] vs. 19% [18/94], difference = 15%, 95% CI 6% to 25%; OR=1.79). Based on the similarity of this research to our own, we anticipate similar screening proportions in our study. To estimate power for the binomial logistic regression analysis on the primary outcome measure (MRR-verified CRC screening), we relied on the sub-analysis from Miller et al.'s data. Importantly, the OR in this analysis (1.79) is consistent with the average effect size of SMS-based interventions on health behaviors (OR=1.81). The G*Power 3.1 program was used to

determine that an odds ratio of 1.79, a two-tailed α error probability of 0.05, and 80% power requires a final sample size of 154 to detect an expected difference in screening rates of 15% at the 6-month follow-up. While unlikely, we will anticipate a conservative 20% attrition rate and set our sample size at 193 (n= 154 post-attrition).

As screening-related health beliefs are important secondary outcomes, we also examined power using treatment effects for screening self-efficacy from the Miller et al. decision aid study. Researchers found that participants in the intervention group reported significantly higher screening self-efficacy (n=223, M=3.89, SD=.84) than control participants (n=227, M=3.64, SD=1.00), $p=.004$. This difference is associated with a Cohen's $d = .27$. To detect a difference of this size in screening self-efficacy, our study will require a final sample size of 110 participants ($\alpha = 0.05$ two-tailed; power = .80). The 154 participants remaining in the analyses post-attrition will be sufficient to detect differences health beliefs across the two survey time points.

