9.4 STATISTICAL ANALYSES

9.4.1 GENERAL APPROACH

Binomial logistic regression will be the main analytic technique for the primary outcome (MRR-verified completion of a recommended CRC screening test). Logistic regression analyses will also examine treatment differences in type of screening received. For secondary outcomes, linear regression will be used. All analyses will control for any confounding variables not managed through randomization (i.e., group difference $p < .10$).

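### The plan states its primary effect both as an odds ratio of 1.79 and as a 15-point difference, which are not the same effect, and plans no absolute estimate with a confidence interval

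*Combined protocol and SAP*

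**What the plan says.** Section 9.1 puts the primary hypothesis on the proportion scale: the intervention arm "will have a higher proportion completing any guideline-concordant colorectal cancer (CRC) screening within 6 months post-randomization". For the null it says "our null hypothesis is that there will be no difference between arms in screening completion at 6 months". It names no effect measure.

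Section 9.2 takes its effect from the nonwhite subgroup of a cited decision-aid trial, given as "34% [33/98] vs. 19% [18/94], difference = 15%, 95% CI 6% to 25%; OR=1.79". It says that power is estimated for the logistic regression on record-verified screening, and that "an odds ratio of 1.79, a two-tailed α error probability of 0.05, and 80% power requires a final sample size of 154". The same sentence continues "to detect an expected difference in screening rates of 15% at the 6-month follow-up".

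Section 9.4.1 says "Binomial logistic regression will be the main analytic technique for the primary outcome" and adds "All analyses will control for any confounding variables not managed through randomization", which it defines as a group difference at p < .10. Section 9.4.2 sets out three treatments of missing outcomes (negative imputation, multiple imputation with 20 datasets, complete cases) but no summary measure. Nothing in Sections 9.1 to 9.4.9 plans a risk difference, a risk ratio or a confidence interval for the comparison of arms.

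**The concern.** The hypothesis asks how many more men are screened, while the planned model answers with an odds ratio. Section 9.2 could have linked the two, but it gives one target in two forms that do not agree. The result could then be judged against either 1.79 or 15 points, and the two give different answers.

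The odds ratio also has a property that the risk difference lacks: it is non-collapsible. With the same proportions screened in each arm, it moves away from 1 when prognostic covariates enter the model. Which covariates enter is known only once baseline imbalance has been seen, so the quantity to be reported is not settled in advance. A health centre deciding whether to adopt the programme needs the absolute gain, and the plan does not provide for estimating it with its uncertainty.

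**Working it through.** **Inputs.** From Section 9.2: 19% (18/94) and 34% (33/98), a 15-point difference, odds ratio 1.79, two-sided 0.05, 80% power, 154 analysed. From Section 9.4.1: the p < .10 entry rule. Covariate strength is not given and is assumed below.

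**1. The plan's own pair of figures.**
- Difference: 0.34 − 0.19 = 0.15. This reproduces.
- Odds ratio: (0.34/0.66)/(0.19/0.81) = 2.20. From the counts, (33/65)/(18/76) = 2.14. Neither is 1.79.
- Ratio of proportions: 0.34/0.19 = 1.79. The stated odds ratio equals this figure.

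**2. What an odds ratio of 1.79 means from 19%.** Odds = 1.79 × 0.19/0.81 = 0.4199. The proportion is 0.4199/1.4199 = 29.6%, a difference of 10.6 points, not 15.

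**3. How far apart the two targets are.** The usual two-proportion formula per arm is [1.96·√(2p̄(1−p̄)) + 0.8416·√(p₁(1−p₁) + p₂(1−p₂))]² / (p₂−p₁)².
- 19% against 34%: (1.2233 + 0.5176)²/0.0225 = 134.7, so 135 per arm and 270 in total.
- 19% against 29.6%: 258 per arm and 516 in total.

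Neither gives 154. The power figure is a separate matter; here the contrast only shows that the two targets are not interchangeable.

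**4. Movement of the odds ratio with covariates.** Let a standard normal prognostic score x have log-odds slope s (assumed). Solve for a₀ and a₁ so that the average of 1/(1+exp(−a−s·x)) over x is 0.19 and 0.34. The conditional odds ratio is exp(a₁−a₀).

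| Assumed slope per SD | Conditional OR | Shift from 2.20 | Risk difference |
|---|---|---|---|
| 0 | 2.20 | – | 15 points |
| 0.5 | 2.28 | 4% | 15 points |
| 1.0 | 2.52 | 15% | 15 points |
| 1.5 | 2.91 | 32% | 15 points |

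The last column is constant by construction: the same men are screened in every row.

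**5. Whether any covariate enters.** If k baseline tests are independent under randomisation, the chance that at least one passes p < .10 is 1 − 0.9^k: 34% for k = 4, 41% for k = 5, 65% for k = 10. The plan does not list the candidates.

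**6. Reading an odds ratio in points.** An odds ratio of 2.2 is 9.6 points at a control rate of 10%, 15.0 at 19%, 18.5 at 30% and 19.5 at 40%. Setting it against 15 points needs a conversion step that the plan does not give.

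**The case against.** Five points can be made for the plan, and most of them limit the concern.

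- **Sizing and analysis share a model.** A reader might infer that the trial was sized purely as a difference in proportions and then analysed on another scale. Section 9.2 does not support that: it names the logistic regression and enters an odds ratio. The fault lies within Section 9.2, where the odds ratio and the 15 points disagree.
- **Adjustment may not happen.** If no variable passes p < .10, the odds ratio is marginal and step 4 does not arise. With independent tests, the chance of that is 66% for 4 candidates and 35% for 10. This stands: the model is possibly adjusted, not certainly.
- **The test is sound on this point.** A reader might infer that the scale mismatch undermines the primary test. It does not. Equal proportions correspond to an odds ratio of 1, so an unadjusted logistic model tests the stated null.
- **Large shifts are assumed.** The entry rule selects on imbalance, not on prognosis, and nothing in the documents shows that strong predictors would enter. At the mildest slope the shift is small.
- **Misreading is not planned.** Taking 2.20 as times as likely overstates 1.79 by 23% (2.196/1.789 = 1.23), but Sections 9.4.1 and 9.4.2 do not say that the result will be reported that way. The crude proportions and their difference can also be read from the counts.

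What survives is that no effect measure is named, the two stated targets conflict, and no absolute estimate with an interval is specified.

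**Conclusion.** The point holds as a gap in specification. The contradiction in Section 9.2 is arithmetic and rests on no assumption beyond the plan's own rates: 15 points goes with an odds ratio of 2.20, and 1.79 goes with 10.6 points. That the plan has no absolute effect with a confidence interval follows from reading Sections 9.1 to 9.4.9.

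The moving target is conditional. It arises only if covariates enter, and its size depends on their strength: about 4% at a slope of 0.5 per SD, up to 32% at 1.5, all under an assumed single normal score.

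It is tempting to conclude that 1.79 is a risk ratio entered by mistake as an odds ratio. The arithmetic fits, but the documents do not say so. The documents also do not support a claim that the primary analysis is invalid or that its odds ratio will be materially inflated. This is an inexpensive improvement that should be made; it does not put the test in doubt.

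**What to change.** Keep the logistic model and its two-sided 0.05 test as the decision rule. In Sections 9.4.1 and 9.4.2, specify the marginal 6-month risk difference with a 95% CI as the effect estimate to set against the 15-point target, reported with the odds ratio:

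1. From the fitted model, predict each randomised man's probability of screening under each arm, average over all randomised men, and subtract.
2. Obtain the variance by the delta method or bootstrap, and combine estimates over the 20 imputed datasets already planned.
3. If no covariate enters, this is the crude difference in proportions, so the estimate has the same meaning whichever way the p < .10 rule falls.

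In Section 9.2, state that an odds ratio of 1.79 and a 15-point difference are different effects, and say which one is the target.

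The cost is wording, a few lines of code and one extra variance calculation; no new data or participants are needed. There are two small downsides. Near 0.05 the logistic p-value and the risk-difference interval may disagree, so the text should say that the logistic test governs. The schema already shows arms of 63 and 65, and Sections 2.1 and 4.1 describe conduct partly in the past tense. If outcome data have been seen, the estimate should be labelled as added late.

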9.2 SAMPLE SIZE DETERMINATION

To determine the adequate sample size for our study, we examined achieved power and treatment effects for a study examining the efficacy of a conceptually similar intervention with an equivalent data analysis plan. Specifically, Miller et al. developed a digital decision aid to help patients select a CRC screening test before a primary care appointment. Compared to controls, participants assigned to the decision aid were twice as likely to get screened at 6-month followup (30% [67/223] vs. 15% [34/227], difference=15%, 95% CI 7% to 23%; OR = 2.5). Follow-up analyses with only nonwhite participants continued to show a significant positive effect on screening (34% [33/98] vs. 19% [18/94], difference = 15%, 95% CI 6% to 25%; OR=1.79). Based on the similarity of this research to our own, we anticipate similar screening proportions in our study. To estimate power for the binomial logistic regression analysis on the primary outcome measure (MRR-verified CRC screening), we relied on the sub-analysis from Miller et al.'s data. Importantly, the OR in this analysis (1.79) is consistent with the average effect size of SMS-based interventions on health behaviors (OR=1.81). The G*Power 3.1 program was used to

determine that an odds ratio of 1.79, a two-tailed α error probability of 0.05, and 80% power requires a final sample size of 154 to detect an expected difference in screening rates of 15% at the 6-month follow-up. While unlikely, we will anticipate a conservative 20% attrition rate and set our sample size at 193 (n= 154 post-attrition).

As screening-related health beliefs are important secondary outcomes, we also examined power using treatment effects for screening self-efficacy from the Miller et al. decision aid study. Researchers found that participants in the intervention group reported significantly higher screening self-efficacy (n=223, M=3.89, SD=.84) than control participants (n=227, M=3.64, SD=1.00), $p=.004$. This difference is associated with a Cohen's $d = .27$. To detect a difference of this size in screening self-efficacy, our study will require a final sample size of 110 participants ($\alpha = 0.05$ two-tailed; power = .80). The 154 participants remaining in the analyses post-attrition will be sufficient to detect differences health beliefs across the two survey time points.

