1.2 SCHEMA

Flow Diagram

Pre-Screening

Total N: 128
Participants who were due for a colorectal screening were contacted by our partner clinic and provided information on the study.

Appointment 1
Day 1

Conduct informed consent process. Perform baseline assessments. See Section 1.3, Schedule of Activities

Randomize

[figure not shown]

Arm 1 (experimental)
N = 63
Mobile SMS+video CRC education intervention

Arm 2 (control)
N = 65
CDC-developed CRC videos via SMS links

Final Assessments
See Section 1.3, Schedule of Activities

Appointment 2
Day ~180

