7.2 PARTICIPANT DISCONTINUATION/WITHDRAWAL FROM THE STUDY

Participants are free to withdraw from participation in the study at any time upon request.

An investigator may discontinue a participant from the study for the following reasons:

- Lost-to-follow up; unable to contact subject
- Participant withdraws consent for further participation and/or data use.
- Participant texts “STOP” to the experimental intervention phone number.
- Safety concerns: any SAE or AE judged related to participation that warrants removal, per the Data and Safety Monitoring Plan and IRB reporting rules.
- Ineligibility discovered post-enrollment, duplicate enrollment, or other protocol violations that compromise data integrity.
- Investigator decision that continued participation poses undue burden or risk (e.g., credible threats of harm), consistent with IRB policies.

The reason for participant discontinuation or withdrawal from the study will be recorded on a dedicated Case Report Form (CRF). Participants who withdraw or are discontinued after randomization will not be replaced; enrollment continues until the target sample size is reached.

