9.3 POPULATIONS FOR ANALYSES

Because randomization carries the expectation of creating treatment groups equivalent with respect to known and unknown prognostic factors, removing randomized participants from the analysis runs the risk of tampering with this balance and introducing bias into the treatment comparisons. As a result, an intention-to-treat analytic approach will be followed such that all participants randomized into the study will be included in all analyses irrespective of protocol violations post randomization. Even with our best efforts, we can expect some missing data. For the primary outcome, missing data will be limited to cases where we are unable to complete an MRR review. Because we will have medical releases for all participants on our primary outcome, very little missing data is anticipated. For secondary measures, missing data will consist of those who fail to complete the 6-month follow-up survey. We will conduct an initial evaluation of missingness by performing a series of logistic regression analyses where the indicator of missing data is the outcome and potential explanatory variables (e.g., condition, screening status, demographic characteristics) serve as predictors. We will then use imputation to manage missing data.

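### Section 9.2 claims 80% power with 154 analysed, but its own rates (34% vs 19%) give about 56% at 154 and 66% at 193; 80% needs about 270, and OR 1.79 does not match a 15-point difference

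*Combined protocol and SAP*

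**What the plan says.** Section 9.2 (Sample Size Determination) takes its effect from the nonwhite sub-analysis of an earlier decision-aid trial, reported as "34% [33/98] vs. 19% [18/94], difference = 15%, 95% CI 6% to 25%; OR=1.79". It says "we anticipate similar screening proportions in our study" and that the sub-analysis was used for the power estimate. G*Power, with an odds ratio of 1.79 and a two-tailed level of 0.05, is then said to show that "80% power requires a final sample size of 154 to detect an expected difference in screening rates of 15" percent. The section allows 20% attrition and so "set our sample size at 193 (n= 154 post-attrition"). It does not give the predictor type or base rate entered in G*Power.

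Sections 4.1 and 6.3 describe balanced permuted blocks in two arms. Section 9.4.1 analyses the primary outcome by logistic regression. Section 9.3 says that "all participants randomized into the study will be included in all analyses irrespective of protocol violations post randomization" and, for the primary outcome, that "very little missing data is anticipated".

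The schema in Section 1.2 shows a total of 128, split 63 and 65. Its text is in the past tense: men due for screening "were contacted by our partner clinic and provided information on the study". Section 7.2 says that "enrollment continues until the target sample size is reached".

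**The concern.** A total of 154 is small for separating 34% from 19% with a binary outcome in two arms. An odds ratio of 1.79 also looks too low for those two rates. This is the only statement of power for the primary test. If it is wrong, readers will take the trial as adequately powered when its own figures say otherwise, and a non-significant result could be read as evidence of no effect.

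**Working it through.** **Inputs.** Section 9.2: p1 = 0.34 (33/98), p2 = 0.19 (18/94), two-sided 0.05 (z = 1.960), 80% power (z = 0.842), 154 analysed, 193 enrolled. Sections 4.1 and 6.3: equal allocation.

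**1. Attrition step.** 154/0.80 = 192.5, so 193. This reproduces.

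**2. Total needed at 34% vs 19%.** With mean rate 0.265,

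n per arm = [1.960·√(2·0.265·0.735) + 0.842·√(0.34·0.66 + 0.19·0.81)]² / 0.15² = (1.2233 + 0.5177)² / 0.0225 = 134.7.

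That is 135 per arm, 270 in total, or 270/0.80 = 337.5, so 338 enrolled at 20% attrition. Other formulas give 264 (unpooled), 268 (arcsine), 278 (Wald on the log odds ratio) and 296 (continuity-corrected). A one-sided test would still need 212. None gives 154.

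**3. Power at the planned sizes.** Power = Φ[(0.15 − 1.960·SE0)/SE1], where SE0 is the pooled and SE1 the unpooled standard error.

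- 77/77: SE0 = 0.0711, SE1 = 0.0701; Φ(0.151) = 56%.
- 97/96: SE0 = 0.0636, SE1 = 0.0626; Φ(0.406) = 66%.

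Simulated logistic regression with a Wald test gives 55% and 66%, and 80% at 270.

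**4. Does OR 1.79 fit 15 points?**

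- Crude odds ratio from the rounded rates: (0.34·0.81)/(0.66·0.19) = 2.20. From the counts: (33·76)/(65·18) = 2.14.
- OR 1.79 from 19%: odds 0.19/0.81 × 1.79 = 0.420, a rate of 29.6% and a difference of 10.6 points.

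**5. Could an unstated base rate explain 154?** Searching all control rates with OR 1.79 and equal arms, the smallest total for 80% power is about 373, at a control rate near 43%. Power at 154 never exceeds about 43%.

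**6. Results by assumption**

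| Assumed effect | Total for 80% | Power at 154 | Power at 193 | Power at 63/65 |
|---|---|---|---|---|
| 34% vs 19% | 270 | 56% | 66% | 49% |
| 33/98 vs 18/94 | 288 | 53% | 63% | 46% |
| 30% vs 15% (cited study, full sample) | 242 | 61% | 71% | 53% |
| OR 1.79 from 19% | 516 | 33% | 40% | 29% |

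From a 19% control rate, the difference detectable with 80% power is about 20 points at 154, 18 at 193 and 22.5 at 128. At 34% vs 19%, the expected half-width of the 95% CI for the risk difference is about 14, 12 and 15 points.

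**7. Where 154 may come from (not established).**

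- The logistic formula for a standard-normal continuous predictor gives (1.960 + 0.842)²/[0.19·0.81·(ln 1.79)²] = 7.849/(0.1539·0.3390) = 150, close to 154, but treatment arm is not such a predictor.
- Converting OR 1.79 to a standardised difference, ln(1.79)·√3/π = 0.321, gives 154 per group in a two-sample t-test, or 308 in total.
- 34/19 = 1.79, so the figure may be a risk ratio (the counts give 1.76). The label alone does not cause the shortfall: in the first formula, 2.20 would give about 82, further from 270.

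**The case against.** The arithmetic is hard to contest, but five points can be raised.

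- **The 1.79 may be a covariate-adjusted odds ratio.** Section 9.2 gives some support: the printed interval of 6% to 25% is narrower than the crude one from 33/98 vs 18/94 (0.145 ± 1.960·0.0625, about 2% to 27%), so the subgroup figures may be model-based or mistranscribed. This stands as a possibility. It does not rescue 154, because no control rate makes 154 sufficient for 1.79 in two equal arms.
- **The planning rates could be the full-sample 30% vs 15%.** The section says the sub-analysis was used, and the full-sample rates still give only 61% and 71%.
- **The 128 is a separate and less certain matter.** It sits in a schema whose figure is not shown, and the title page, where the protocol says a summary of changes is kept, was not available. The sentence in Section 7.2 also concerns non-replacement of withdrawals. This stands: 128 only reads as achieved enrolment, and the main finding does not depend on it.
- **Interpreting a null result from the confidence interval is good practice, not a correction of Section 9.2.** This is fair; it is an addition.
- **If conduct is complete, restating power changes no enrolment, endpoint or test.** True, but the power statement will still be read beside the results.

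**Conclusion.** The concern holds. At the plan's own rates, equal allocation and two-sided 0.05, 154 analysed gives about 56% power, not 80%. Analysing all 193, the more favourable reading under Section 9.3, gives about 66%. The shortfall against 270 is 116 participants at 154 and 77 at 193. The risk of missing the planned effect is about 44% or 34%, against the stated 20%. Separately, OR 1.79 and a 15-point difference from 19% cannot both be the planning effect.

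These figures assume an unadjusted comparison. Section 9.2 mentions no covariates, and Section 9.4.1 adjusts only for variables found imbalanced at p < .10. The size varies with the rates used, but every reading of the documents falls short of 80%. The origin of 154 and the meaning of 1.79 remain unknown.

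**What to change.** In Section 9.2, withdraw the 80% claim and restate power from one set of rates, for example:

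> Assuming 34% vs 19% (odds ratio 2.20), 1:1 allocation and a two-sided 0.05 level, power is about 56% with 154 analysed and about 66% with all 193 analysed. From a 19% control rate, the difference detectable with 80% power is about 20 and 18 points respectively.

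In addition:

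- State whether 1.79 is an odds ratio or a risk ratio, crude or adjusted, and its source; otherwise remove it.
- If 154 is kept as a record of how the target was set, label it as such and give the G*Power predictor type and base rate.
- In Section 1.2 or 9.2, say whether 128 is achieved enrolment and, if so, why it is below 193. Report the corresponding 49% power and 22.5-point detectable difference as a separate, dated statement.
- State that a non-significant primary result will be interpreted from the 95% CI of the risk difference.

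The cost is wording in two sections and a less favourable stated power. No enrolment, endpoint or test changes.
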